 - u If the patient discontinues treatment without having PD, tumor assessment/imaging should continue to be performed per standard of care until progression, withdrawal of consent, subsequent treatment, or the study is stopped. Follow-up for progression may be done by review of medical records every 3 months to confirm patient status.
 - v- All patients in Part Z will have an on-treatment biopsy in Cycle 2 between Days 1-7 unless not technically feasible or unsafe for the patient after discussion with the Medical Monitor.

CONFIDENTIAL

LIST OF ABBREVIATIONS

Abbreviation or special term	Explanation
ADA	Anti-drug antibody
ADC	Antibody drug conjugate
AE	Adverse event
ALT	Alanine aminotransferase
ANC	Absolute neutrophil count
AR	Adverse reaction
AST	Aspartate aminotransferase
CFR	Code of Federal Regulations
CI	Confidence interval
CR	Complete response
cfRNA	Cell-free RNA
CT	Computed tomography
CTCAE	Common Terminology Criteria for Adverse Events
ctDNA	Circulation-tumor DNA
Development Innovations	Sarah Cannon Development Innovations, LLC
DMC	Data Monitoring Committee
DoR	Duration of response
ECG	Electrocardiogram
ECOG	Eastern Cooperative Oncology Group
eCRF	Electronic Case Report Form
EOT	End-of-treatment (visit)
FDA	Food and Drug Administration
FISH	Fluorescence in situ hybridization
GCP	Good Clinical Practice
HER3	Receptor tyrosine-protein kinase erbB-3
HIPAA	Health Insurance Portability and Accountability Act
HR	Hormone receptor
IB	Investigator's Brochure
ICF	Informed consent form
ICH	International Council for Harmonisation
IHC	Immunohistochemistry
ILD	Interstitial lung disease
IND	Investigational New Drug
IRB	Institutional Review Board
ISF	Investigator study file
IV	Intravenous
MBC	Metastatic breast cancer
MRI	Magnetic resonance imaging
NCI	National Cancer Institute
ORR	Overall response rate

CONFIDENTIAL

Abbreviation or special term	Explanation
PD	Progressive disease
PFS	Progression-free survival
PHI	Protected health information
PK	Pharmacokinetic
PR	Partial response
QT	ECG interval measured from the onset of the QRS complex to the end of the T wave
QTc	QT interval corrected for heart rate
RECIST	Response Evaluation Criteria in Solid Tumors
SAE	Serious adverse event
SAP	Statistical Analysis Plan
SAR	Suspected adverse reaction
SCRI	Sarah Cannon Research Institute
SD	Stable disease
SOA	Schedule of Assessments
SUSAR	Suspected unexpected serious adverse reaction
TEAE	Treatment-emergent adverse events
T-DXd	Trastuzumab deruxtecan

1. INTRODUCTION

1.1 Background and Study Rationale

1.1.1 HER3

Receptor tyrosine-protein kinase erbB-3 (HER3) protein that is encoded by the *ERBB3* oncogene is highly expressed in many cancers, including breast cancer (Lee-Hoeflich et al. 2008). Unlike the other members of the HER family, HER3 is unique in that it has minimal intrinsic kinase activity. The HER3 receptor forms heterodimers with other RTKs, most notably with HER2, and the subsequent downstream signaling promotes tumorigenesis and metastasis (Mota et al. 2017; Mishra et al. 2018; Lyu et al. 2018).

The heterodimerization of HER3 with RTKs activates oncogenic signaling via the PI3K/Akt and the MAPK/ERK and other pathways. Inhibition of these pathways using MEKi, PI3Ki, mTOR and AKTi leads to HER3 upregulation (Gala & Chandarlapaty 2014). This upregulation leads to sustained PI3K/AKT signaling, resulting in tumor survival (Gala & Chandarlapaty 2014; Mishra et al. 2018).

Increased levels of circulating HER3 ligand HRG may also lead to HER3 activation and treatment resistance. Multiple studies indicate that HER3 activation plays a key role in treatment resistance to EGFR and anti-estrogen therapies. Fulvestrant resistant MC-7 cells were shown to be dependent on HER3 and NRG-2 (a HER3 ligand) expression for sustained growth and survival (Frogne T et al. 2009). Activation of the PI3K/Akt pathway and proto-oncogene SRC signaling are major determinants of trastuzumab-induced resistance based on data from preclinical studies (Mishra et al. 2018). Thus HER3 appears to play an important role in both HER2+ and ER+ breast cancer. Furthermore, HER3 has been shown to be upregulated in chemotherapy-resistant breast cancer. Finally, a meta-analysis across multiple tumor types demonstrated that higher expression of HER3 correlates with poorer outcomes in cancer patients (Ocana et al. 2013).

Thus HER3 is a valid therapeutic target in cancer and drugs targeting HER3 have employed different strategies. These include mono- and bi-specific antibodies targeting multiple HER3 domains, bi-specific ligand traps for HER3, small molecule inhibitors against HER3 pseudokinase activity and HER3 peptide vaccines, which are in various stages of clinical development.

1.1.2 U3-1402 (patritumab deruxtecan)

Patritumab deruxtecan is an antibody drug conjugate (ADC) comprising a recombinant fully human anti-HER3 IgG1 monoclonal antibody (patritumab, U3-1287) covalently linked to MAAA-1162a (glycine-glycinephenylalanine-glycine [GGFG]) tetrapeptide linker containing a topoisomerase I inhibitor [MAAA-1181a]). MAAA-1181a is released after internalization and leads to apoptosis of the target tumor cells via the inhibition of topoisomerase I. Patritumab deruxtecan has exhibited specific binding activity to human HER3.

1.1.3 Clinical Safety

The safety and preliminary efficacy of patritumab deruxtecan were evaluated in the on-going Phase I/II Study U31402-A-J101 in US and Japan in patients with metastatic breast cancer (MBC). The trial enrolled advanced/unresectable MBC patients (irrespective of subtype) with HER3 positive tumors who were refractory/intolerant to standard therapy in the dose escalation

CONFIDENTIAL

phase. Patients with HER3-positive MBC who had received ≥ 2 and ≤ 6 prior chemotherapy regimens were then enrolled in the dose-finding phase and subsequent expansion phase. The expansion phase included HR+/HER2- and triple negative MBC patients with HER3 high expression and HR+/HER2- MBC patients with HER3 low expression. Two different doses of patritumab deruxtecan, 4.8 mg/kg and 6.4 mg/kg, were evaluated.

As of the data cut-off date of 05 August 2019, 144 of 145 patients enrolled in Study U31402-A-J101 had received patritumab deruxtecan: 34 patients in the dose escalation part, 32 patients in the dose-finding part, and 78 patients in the dose expansion part. A total of 141 (97.9%) patients had experienced at least 1 treatment-emergent adverse event (TEAE) and 138 (95.8%) patients had experienced at least 1 TEAE considered related to study drug by the Investigator. The most frequent TEAEs (in $>20\%$ of patients), all grades, regardless of causality and noted in descending order of frequency, included nausea (113 [78.5%] patients), decreased appetite (74 [51.4%] patients), platelet count decreased (65 [45.1%] patients), neutrophil count decreased (61 [42.4%] patients), vomiting (57 [39.6%] patients), white blood cell count decreased (53 [36.8%] patients), anemia (52 [36.1%] patients), diarrhea (50 [34.7%] patients), aspartate aminotransferase (AST) increased (41 [28.5%] patients), fatigue (40 [27.8%] patients), alanine aminotransferase (ALT) increased (36 [25.0%] patients), stomatitis (36 [25.0%] patients), constipation (32 [22.2%] patients), and alopecia and malaise (31 [21.5%] patients each).

There were 92 (63.9%) patients with TEAEs of Grade 3 or higher, including most commonly (in $>5\%$ of patients), neutrophil count decreased (37 [25.7%] patients), platelet count decreased (32 [22.2%] patients), anemia (25 [17.4%] patients), white blood cell count decreased (21 [14.6%] patients), thrombocytopenia (12 [8.3%] patients), neutropenia (11 [7.6%] patients), hypokalemia (10 [6.9%] patients), and AST increased (8 [5.6%] patients).

Forty-six (31.9%) of the 144 treated patients had a treatment-emergent serious adverse event (SAE), including 31 (21.5%) patients with study drug-related SAEs. The most common SAEs reported in more than 1 patient, in descending order of frequency, included platelet count decreased (8 [5.6%] patients); vomiting (6 [4.2%] patients); decreased appetite (5 [3.5%] patients); nausea and thrombocytopenia (4 [2.8%] patients each); pneumonitis (3 [2.1%] patients); and febrile neutropenia, mental status changes, and urinary tract infection (2 [1.4%] patients each).

Treatment-emergent AEs were associated with a dose interruption in 68 (47.2%) patients and a dose reduction in 22 (15.3%) patients. Twelve (8.3%) patients discontinued study drug due to a TEAE.

Ten (6.9%) of the 144 treated patients experienced a potential interstitial lung disease (ILD) event (1 per patient) requiring ILD adjudication as of the data cut-off date, including 6 (4.2%) patients with pneumonitis (3 Grade 2 and 3 Grade 3), and 4 (2.8%) patients (1 patient each) with ILD (Grade 2), radiation pneumonitis (Grade 3), radiation fibrosis-lung (Grade 1), and respiratory failure (Grade 2). Treatment-emergent AEs in 7 of the above 10 patients (6 pneumonitis and 1 ILD) were considered as related to patritumab deruxtecan by the Investigators.

CONFIDENTIAL

1.1.4 Clinical Efficacy

As of the data cut-off date of 06 November 2018, the median follow-up time was 10.5 months for patients with MBC (N=42, the dose escalation phase and the dose finding phase, 1.6 to 8.0 mg/kg) in Study U31402-A-J101. The preliminary efficacy reported on treatment with single agent patritumab deruxtecan per Investigator assessment showed an ORR of 42.9% (4.8 mg/kg: 40.0% [6/15], 6.4 mg/kg: 60.0% [9/15]). The median progression-free survival (PFS) was 8.3 months (range: 1.2, 16.8+), median duration of response (DoR) was not reached (range: 2.8, 13.8+).

1.1.5 Study Rationale

The safety and preliminary efficacy reported with single agent patritumab deruxtecan in Study U31402-A-J101 and benefit/risk balance support further exploration of patritumab deruxtecan in the MBC patient population to determine the subset of patients that are likely to derive the greatest benefit.

As noted above, HER3 is an important dimerization partner for HER2 and this heterodimerization leads to oncogenic signaling via the PI3K/Akt and the MAPK/ERK and other pathways. Trastuzumab deruxtecan (DS-8201a) is a HER2-targeted ADC with a topoisomerase 1 inhibitor as the payload. Trastuzumab deruxtecan has revolutionized the treatment of HER2+ MBC by significantly prolonging PFS in heavily pretreated and 3L HER2+ MBC (Modi et al. 2020; Cortes et al. 2022).

There are multiple ADCs in development against novel targets like Trop 2, Nectin 4, and HER3 with either similar or novel payloads. The efficacy of ADCs with a similar payload directed against a novel target is unknown; hence it is of interest to evaluate patritumab deruxtecan, a HER3-targeted ADC with topoisomerase 1 inhibitor as the payload, in a patient population whose disease has progressed on an ADC. Recent research highlights both cross-resistance to an ADC after ADC therapy in patients with MBC and durable responses on latter lines of ADC therapy, particularly if a different antibody target is utilized. Further research is needed to understand the mechanisms of clinical resistance and to guide optimal sequencing of ADC-based treatment options (Abelman et al. 2023).

1.2 Potential Risks and Benefits of the Treatment Regimen

Patritumab deruxtecan is being developed for the treatment of HER3-expressing malignant tumors. The product is in the early stages of development.

Nonclinical studies have demonstrated the antitumor activity of patritumab deruxtecan in HER3 tumor-bearing mouse models. Thus, patritumab deruxtecan is hypothesized to demonstrate efficacy in treating HER3-expressing tumors in patients.

Based on the preliminary clinical safety data from the ongoing patritumab deruxtecan studies, nausea, decreased appetite, platelet count decreased/thrombocytopenia, white blood cell count decreased/leukopenia, neutrophil count decreased/neutropenia, vomiting, anemia, diarrhea, fatigue, malaise, stomatitis, constipation, ALT increased, AST increased, and alopecia are identified risks and will continue to be closely monitored and evaluated in the patritumab deruxtecan clinical development program.

Based on clinical data and safety information available as of the 05 August 2019 data cut-off, ILD/pneumonitis was added as an adverse drug reaction associated with the use of patritumab

CONFIDENTIAL

deruxtecan and considered an important identified risk. The reported ILD events were generally manageable via close monitoring and by following the ILD management plan in the protocol.

In conclusion, based on the efficacy and safety data from the nonclinical studies and the preliminary clinical safety data from ongoing studies, the benefit/risk balance supports continued clinical development of patritumab deruxtecan. For more information on the non-clinical and clinical studies, see the current patritumab deruxtecan Investigator’s Brochure (IB).

1.3 Rationale for the dose

The regimen to be evaluated will be a fixed dose of 5.6 mg/kg administered as a continuous IV infusion on Day 1 of each 21-day cycle.

Data from two studies have been considered for the selection of the 5.6 mg/kg dose. Study U31402-A-J101 included 1.6 mg/kg, 3.2 mg/kg, 6.4 mg/kg and 8.0 mg/kg Q3W in subjects with breast cancer, the MTD was established at 6.4 mg/kg. Study U31402-A-U102 included 3.2 mg/kg, 4.8 mg/kg, 5.6 mg/kg and 6.4 mg/kg Q3W in NSCLC patients, the MTD was established at 5.6 mg/kg. In addition, 4.2 mg/kg every 2 weeks and an up-titration dose regimen were studied in the J101 study, with 3.2 mg/kg in Cycle 1, 4.8 mg/kg in Cycle 2, and 6.4 mg/kg in Cycle 3 and after. Exposure of intact patritumab deruxtecan ADC, total anti-HER3 antibody and released payload MAAA-1181a increased as dose increased. Population pharmacokinetics (PK), and exposure response analyses for efficacy and safety were conducted using data from both the J101 and U102 studies. Exposure-efficacy relationship was established for intact patritumab deruxtecan ADC and the exposure safety relationship was established for released payload MAAA-1181a.

The rationale for the selection of 5.6 mg/kg is based on an exposure-response analysis of efficacy, and 5.6 mg/kg is predicted to provide a lower probability of ≥Grade 3 thrombocytopenia compared to 6.4 mg/kg, and an improved ORR compared to 4.8 mg/kg. More data are being collected in the ongoing patritumab deruxtecan studies to further evaluate this dosing regimen.

2. STUDY OBJECTIVES AND ENDPOINTS

Table 1 Study Objectives and Corresponding Endpoints

Objectives:	Endpoints/Variables:
Primary Objective:	Endpoints/Variables:
Evaluate ORR and PFS-6 of single agent patritumab deruxtecan in patients with HER2-MBC	ORR defined as the proportion of patients with confirmed CR or PR (i.e., confirmation at least 4 weeks apart) and 6-month PFS as defined by defined as the proportion of patients who survive progression-free for at least 6 months per RECIST version (v) 1.1.

Objectives:	Endpoints/Variables:
Secondary Objectives:	Endpoints/Variables:
Assess the safety and tolerability of patritumab deruxtecan in patients with MBC	AEs/SAEs Vital signs Clinical chemistry/hematology parameters ECGs
Estimate the DoR	Duration of response
PFS in patients with MBC	PFS
Clinical Benefit Rate (CBR)	CBR defined as the proportion of patients with CR, PR or best overall response of SD for ≥ 6 months according to the RECIST v 1.1 criteria.
Evaluate ORR and PFS-6 of single agent patritumab deruxtecan in patients with HER2+ MBC after progression on trastuzumab deruxtecan	ORR defined as the proportion of patients with confirmed CR or PR (i.e., confirmation at least 4 weeks apart) and 6-month PFS as defined by defined as the proportion of patients who survive progression-free for at least 6 months per RECIST version (v) 1.1.
Exploratory Objectives:	Endpoints/Variables:
Evaluate HER3 protein expression and its relationship with efficacy	HER3 protein expression, ORR, PFS-6
Identify biomarkers associated with clinical efficacy in patients with MBC	Assays of these samples will include HER3 protein expression, and immune cell markers.
Evaluate PK (pharmacokinetics) and ADA (anti-drug antibody) in patients with MBC	Serum concentration of patritumab deruxtecan (antibody conjugated MAAA-1181a, total anti-HER3 antibody, and MAAA-1181a) and population PK analysis and incidence and titer of ADA in serum via validated assay

AE = adverse event; DoR = duration of response; ECG = electrocardiogram; MBC = metastatic breast cancer; ORR = Overall response rate; PFS = progression-free survival; RECIST = Response Evaluation Criteria in Solid Tumors; SAE = serious adverse event

3. STUDY PATIENT POPULATION AND DISCONTINUATION

3.1 Inclusion Criteria

Patients must meet the following criteria in order to be included in the research study:

3.1.1 Inclusion criteria for Part A and B (HER2-negative) and Part Z (HER2-positive) cohorts:

1. Written informed consent, according to local guidelines, signed and dated by the patient or by a legal guardian prior to the performance of any study-specific procedures, sampling, or analyses

CONFIDENTIAL

2. Women and men at least 18 years-of-age at the time of signature of the informed consent form (ICF)
3. Histologically documented locally advanced or metastatic breast cancer
4. Triple-negative breast cancer (TNBC) patients should have received at least 1 but no more than 5 prior lines of chemotherapy in the metastatic setting
5. **Parts A and B patients only:** Patients with HR+ HER2-negative MBC should have received prior treatment with endocrine therapy +CDK 4/6 inhibitor. No limit to prior endocrine therapy regimens, but no more than 2 prior chemotherapy regimens in the metastatic setting are allowed. HR+ = ER and/or PgR positivity that are defined as $\geq 1\%$ of cells expressing HR via IHC analysis. HER2 negativity is defined as either of the following: IHC 0, IHC 1+, or IHC 2+/in situ hybridization (ISH) negative.
6. **Part B patients only:** Patients with HER2-negative MBC will be included into one of the following 2 subgroups: 1) MBC HR+, HER2-, regardless of HER3 expression, who have received trastuzumab deruxtecan and/or sacituzumab govitecan, or, 2) mTNBC, regardless of HER3 expression, who have received sacituzumab govitecan and/or datopotamab deruxtecan.
7. **Part Z patients only:** should have documented HER2-positive expression as per American Society of Clinical Oncology – College of American Pathologists guidelines based on local testing.
8. **Part Z patients only:** should have had prior treatment with at least 2 anti-HER2 therapies, 1 of which must be trastuzumab deruxtecan. These patients must have experienced disease progression after receiving trastuzumab deruxtecan.
9. At least 1 measurable lesion per Response Evaluation Criteria in Solid Tumors (RECIST) v1.1 (bone-only disease excluded)
10. Patients who have received radiation or surgery for brain metastases are eligible if therapy was completed ≥ 4 weeks prior to initiation of study treatment (2 weeks for patients who received palliative radiation therapy), there is no evidence of central nervous system disease progression on a scan or mild neurologic symptoms, and there is no requirement for chronic corticosteroid therapy for the treatment of brain metastases.
11. Willingness to undergo pre-treatment biopsy and on-treatment biopsies. Must have a tumor amenable to pre-treatment biopsy (unless archived tissue is available and was obtained within 2 months prior to starting treatment) and on-treatment biopsy (excludes bone lesions and previously irradiated lesions).
12. Eastern Cooperative Oncology Group (ECOG) Performance Status score of 0 or 1 (Appendix A)

CONFIDENTIAL

13. Has adequate organ function within 7 days before the start of study treatment, defined as:

- Platelet count $\geq 100 \times 10^9/L$
- Hemoglobin (Hb) ≥ 9 g/dL (transfusion and/or growth factor support allowed)
- Absolute neutrophil count $\geq 1.5 \times 10^9/L$
- Prothrombin time (PT) and partial thromboplastin time (PTT) $\leq 1.5 \times$ the upper limit of normal (ULN), except for patients on coumadin-derivative anticoagulants or other similar anticoagulant therapy, who must have PT-international normalized ratio (INR) within therapeutic range as deemed appropriate by the Investigator.
- Serum creatinine $\leq 1.5 \times$ ULN, or creatinine clearance ≥ 50 mL/min as calculated using the modified Cockcroft-Gault equation; confirmation of creatinine clearance is only required when creatinine is $>1.5 \times$ ULN.
- AST/ALT $\leq 3 \times$ ULN (if liver metastases are present, $\leq 5 \times$ ULN)
- Total bilirubin $\leq 1.5 \times$ ULN if no liver metastases or $<3 \times$ ULN in the presence of documented Gilbert's syndrome or liver metastases
- Serum albumin ≥ 2.5 g/dL

14. Male patients with female partners of childbearing potential and female patients of childbearing potential are required to use two forms of acceptable contraception (Appendix C), including one barrier method, during their participation in the study and for at least 7 months following last dose. Male patients must also refrain from donating sperm during their participation in the study.

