6. Leptomeningeal metastases or evidence of spinal cord compression or brain metastases, defined as being clinically active and symptomatic, or requiring therapy with corticosteroids or anticonvulsants to control associated symptoms. Patients with clinically inactive or treated brain metastases who are asymptomatic (i.e., without neurologic signs or symptoms and do not require treatment with corticosteroids or anticonvulsants) may be included in the study. Patients must have a stable neurologic status for at least 2 weeks prior to Cycle 1 Day 1.
7. Women who are pregnant, nursing, or plan to become pregnant while in the study and for at least 7 months after the last administration of study treatment
8. Men who plan to father a child while in the study and for at least 7 months after the last administration of study treatment
9. Uncontrolled or significant cardiovascular disorder prior to Cycle 1 Day 1, including:
 - Mean resting corrected QT interval using Fridericia's formula (QTcF) prolongation to >470 ms for females and >450 ms for males in three successive screening measurements
 - Patients with a left ventricular ejection fraction (LVEF) <50%
 - Resting systolic blood pressure >180 mmHg or diastolic blood pressure >110 mmHg).
 - Documented myocardial infarction within 6 months.
 - Congestive heart failure (New York Heart Association ≥ Grade 2 [Appendix D]) within 28 days
10. Has known clinically significant corneal disease from prior therapies such as drug-induced keratitis
11. Is receiving chronic systemic corticosteroids dosed at >10 mg prednisone or equivalent anti-inflammatory activity or any form of immunosuppressive therapy prior to Cycle 1

CONFIDENTIAL

Day 1. Patients who require use of bronchodilators, inhaled or topical steroids, or local steroid injections may be included in the study.

12. As judged by the Investigator, any evidence of severe or uncontrolled systemic diseases, including uncontrolled hypertension, uncontrolled diabetes mellitus, active bleeding diatheses, or active infection, including hepatitis B, hepatitis C, and human immunodeficiency virus. Screening for chronic conditions is not required.
13. Presence of other active invasive cancers other than the one treated in this study within 3 years prior to screening, except appropriately treated basal cell carcinoma of the skin, in situ carcinoma of uterine cervix, or other local tumors considered cured by local treatment

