3.3 Discontinuation from Study Treatment

Patients will be discontinued from study treatment for any of the following reasons:

- Disease progression (Patients who are receiving clinical benefit in the opinion of the treating Investigator may be allowed to stay on study after consultation with the Medical Monitor.)
- Irreversible or intolerable toxicity or abnormal laboratory values thought to be related to drug toxicity
- Conditions requiring therapeutic intervention not permitted by the protocol
- Intercurrent illness (this will be at the Investigator's discretion)
- Inability of the patient to comply with study requirements
- Patient lost to follow-up
- Patient requests to discontinue treatment
- Patient withdraws consent from study treatment or study participation altogether
- Pregnancy
- Study termination

After discontinuation from protocol treatment, patients must be followed for adverse events (AEs) for 40 days (+7 days) after their last dose of study drug. All new AEs occurring during this period must be reported and followed until resolution, unless, in the opinion of the Investigator, these values are not likely to improve because of the underlying disease. In this case, the Investigator must record his or her reasoning for this decision in the patient's medical records.

All patients who have Grade 3 or 4 laboratory abnormalities (per National Cancer Institute [NCI] CTCAE Version 5.0) at the time of discontinuation must be followed until the laboratory values have returned to Grade 1 or 2, unless it is, in the opinion of the Investigator, not likely that these values are to improve. In this case, the Investigator must record his or her reasoning for making this decision in the patient's medical records.

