6. DOSE MODIFICATIONS

If toxicity occurs, the toxicity will be graded using the NCI CTCAE Version 5.0, and appropriate supportive care treatment will be administered to decrease the signs and symptoms thereof. Dose adjustments will be based on the organ system exhibiting the greatest degree of toxicity.

Doses of patritumab deruxtecan will be modified based on hematologic and non-hematologic toxicity. If dose reductions are necessary, they will be permanent for the remainder of the treatment. Any patient requiring a toxicity-related dose delay of more than 18 weeks (126 days) from the last patritumab deruxtecan dose must be discontinued from the study, unless discussed with the Medical Monitor for extenuating circumstances. During the time of any dose delay, scheduled CT/MRI scans should continue as per protocol, and subjects should fulfill all of the following criteria:

- Study drug may be resumed with confirmation of continued benefit per RECIST 1.1. Scans should be performed at the frequency defined per protocol while the drug is being held.
- At minimum, 1 restaging scan must be done within 6 weeks prior to restarting the study drug.
- Investigational product is restarted within the guidance of the treatment management guidelines for patritumab deruxtecan, if appropriate.
- No prohibited concomitant medications have been administered since the last dose of patritumab deruxtecan.

If toxicities occur that are \leq Grade 2, they should be managed symptomatically, if possible, and the patient should be re-treated without a dose reduction. If toxicities occur that are \geq Grade 3, treatment should be withheld until resolution to \leq Grade 1 or to the baseline value (if the baseline value was $>$ Grade 1). Treatment should then be re-instituted, if medically appropriate, at the next lower dose level (see Table 2).

The dose level reductions to be used in this study are presented in Table 2.

CONFIDENTIAL

Table 2 Dose Level Modifications

Dose Level	Patritumab deruxtecan
Starting Dose	5.6 mg/kg
Dose Level -1	4.8 mg/kg
Dose Level -2	3.2 mg/kg

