7.4.2 Forty-Day Safety Follow-Up

All patients will be followed after discontinuing study treatment until all treatment-related toxicity resolves or for at least 40 days (+7 days) post-study drug discontinuation or until the start of another anti-cancer treatment. Any concomitant medications received up to 30 days after the last dose of study medication should be recorded.

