7.4.3 Progression-free Survival Follow-Up

If the patient discontinues treatment without having PD, tumor assessment/imaging should continue to be performed per standard of care until progression, withdrawal of consent, subsequent treatment, or the study is stopped. Follow-up for progression may be done by review of medical records every 3 months to confirm patient status.

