Appendix C: Guidelines for Women of Childbearing Potential and Fertile Male Patients

Acceptable Contraception Methods:

Women of childbearing potential, defined as all women physiologically capable of becoming pregnant, must use highly effective contraception during the study and for 7 months after stopping treatment.

Highly effective contraception is defined as either:

True Abstinence When this is in line with the preferred and usual lifestyle of the patient. Periodic abstinence (e.g., calendar, ovulation, symptothermal, post-ovulation methods) and withdrawal are not acceptable methods of contraception.

Sterilization When a woman of childbearing potential has had surgical bilateral oophorectomy (with or without hysterectomy) or tubal ligation at least six weeks prior to study entry. In case of oophorectomy alone, only when the reproductive status of the woman has been confirmed by follow-up hormone level assessment.

Male Partner Sterilization When there is appropriate post-vasectomy documentation of the absence of sperm in the ejaculate.

Use of a combination of any two of the following (one from a + one from b):

- a) Placement of an intrauterine device (IUD) or intrauterine system (IUS) or established use of oral, injected or implanted hormonal methods of contraception.
- b) Barrier methods of contraception: condom or occlusive cap (diaphragm or cervical/vault caps) with spermicidal foam/gel/film/cream/vaginal suppository.

Fertile male patients, defined as all males physiologically capable of conceiving offspring, with female partners of childbearing potential must use condoms plus spermicidal agent during the study treatment period and for 7 months after the last dose of the study drug, and should not father a child during this period.

Male patients must also refrain from donating sperm during their participation in the study.

Unacceptable Contraception Methods for women of childbearing potential include:

- IUD progesterone T
- Female condom
- Natural family planning (rhythm method) or breast-feeding
- Fertility awareness
- Withdrawal
- Cervical shield

CONFIDENTIAL

Pregnancies

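### The ban on sperm donation stops at the end of study participation and lacks the 7-month post-dose period that the protocol sets for male contraception and for not fathering a child.

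*Combined protocol and SAP*

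**What the plan says.** Sperm donation is addressed in three places with the same sentence: synopsis inclusion criterion 14, Section 3.1.1 inclusion criterion 14, and Appendix C. It reads "Male patients must also refrain from donating sperm during their participation in the study".

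The other male reproductive precautions run longer:

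- **Contraception (criterion 14, the sentence just before):** two methods, "including one barrier method, during their participation in the study and for at least 7 months following last dose".
- **Appendix C, fertile men with female partners of childbearing potential:** condom plus spermicide during treatment "and for 7 months after the last dose of the study drug, and should not father a child during this period".
- **Exclusion criterion 8 (Section 3.2.1 and synopsis):** keeps out "Men who plan to father a child while in the study and for at least 7 months after the last administration" of study treatment.

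Participation has no patient-level end date. Section 5.2 defines the end of the study only for the trial as a whole. After treatment, Section 3.3 says "patients must be followed for adverse events (AEs) for 40 days (+7 days) after their last dose of study drug". Section 7.4.2 follows patients until treatment-related toxicity resolves, or "for at least 40 days (+7 days) post-study drug discontinuation or until the start of another anti-cancer treatment". Section 7.4.3 applies only to patients who stop without progressive disease; for them "tumor assessment/imaging should continue to be performed per standard of care until progression, withdrawal of consent, subsequent treatment, or the study is stopped".

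**The concern.** The protocol sets a 7-month precaution period after the last dose for conception by male patients, and the study drug carries a topoisomerase I inhibitor payload (Section 1.1.2). Donated sperm is another route to conception, and the text gives no reason for a shorter period. Yet the donation rule ends with participation, which can end well before month 7. A man could then donate inside that period without breaching the protocol. The person exposed would be a third party outside the study.

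This is a gap in coverage, not a contradiction. The three donation sentences agree with one another, and all the rules can be followed at once. The stake is reproductive safety wording only.

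**Working it through.** No trial figure needs reproducing. The check compares the rules and then measures the uncovered time.

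**1. Does participation already include the 7 months?** No. Criterion 14 names participation and the 7 months after the last dose as two periods joined by a conjunction. If the first contained the second, the second would be redundant. The follow-up provisions also give no 7-month minimum: safety follow-up has a floor of 40 (+7) days, and follow-up for progression applies only to patients without progression and can end at any of four events.

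**2. Do other rules close the gap?**

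| Rule | Who it reaches | Period | Covers donation after participation? |
|---|---|---|---|
| Criterion 14, donation sentence | all male patients | participation | no |
| Criterion 14, contraception | men with female partners of childbearing potential | participation plus at least 7 months | not addressed |
| Appendix C, not fathering a child | fertile men with such partners | treatment plus 7 months | in part; only these men |
| Exclusion criterion 8 | men with a plan at entry to father a child | study plus at least 7 months | only through a plan held at entry |

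What remains is mainly a man outside the partner clause, with no such plan at entry, who leaves before month 7.

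**3. Can he leave before month 7?** Yes. A patient who stops at progression has no follow-up under Section 7.4.3. The start of another anti-cancer treatment ends follow-up under both Sections 7.4.2 and 7.4.3. He may also withdraw consent.

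**4. How long is the uncovered time?** Uncovered days = 7 months − days from last dose to end of participation, with a minimum of 0.

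7 months = 7 × 365.25 / 12 = 213.1 days.

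| When participation ends | Arithmetic | Uncovered |
|---|---|---|
| 40 days after last dose (Section 3.3) | 213.1 − 40 | 173.1 days (5.7 months) |
| 47 days after last dose (40 + 7) | 213.1 − 47 | 166.1 days (5.5 months) |
| Treatment stopped after a 126-day hold, then 40 days from discontinuation (Sections 6 and 7.4.2) | 213.1 − 126 − 40 | 47.1 days |
| Same, then 47 days | 213.1 − 126 − 47 | 40.1 days |
| Another anti-cancer treatment 21 days after last dose (assumed day, one cycle) | 213.1 − 21 | 192.1 days (6.3 months) |
| At the last dose | 213.1 − 0 | 213.1 days |
| 7 months or more after last dose | minimum of 0 | 0 days |

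The 126 days is the longest routine hold: a patient with a "toxicity-related dose delay of more than 18 weeks (126 days) from the last patritumab deruxtecan dose must be discontinued" from the study unless the Medical Monitor agrees otherwise. The 0-day case can arise when toxicity follow-up or follow-up for progression is long, or when the patient stays on study after progression (Section 5).

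**The case against.** The strongest reply is that no error is shown. The same sentence appears three times, so it may be a deliberate rule; nothing in the documents says donation and contraception must share one period, and the basis for the 7 months is not given. It remains possible that a shorter donation period is intended. But no reason for one is stated, and the medical team can settle the point in a sentence.

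Second, most of the risk is already handled. Exclusion criterion 8 reaches every man whatever his partner status and could be read to include a plan to conceive through donated sperm. Appendix C covers fertile men with partners of childbearing potential. This narrows the group, as the comparison above reflects, but criterion 8 tests a plan at entry, not later conduct, and Appendix C is limited by partner status.

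Third, the Investigator's Brochure (to which Section 8.1.3 refers for precautions) and the consent form were not available, so patients may in practice be given the longer instruction. That stands. The point is about the protocol text alone.

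Fourth, the size is loose. The range of 0 to about 213 days is the whole possible range. The early-switch figure relies on Section 7.4.2, whereas Section 3.3 requires 40 (+7) days of adverse event follow-up with no exception for new therapy, and Schedule of Assessments footnote t asks for the 40-day visit before new treatment. The 126-day case depends on counting from discontinuation, where Section 3.3 counts from the last dose. These criticisms are fair. The 166 to 173 day figure is the most useful illustration, and it too is conditional.

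**Conclusion.** The concern holds. As written, the donation rule is shorter than the protocol's own 7-month precaution period, and no other provision fully closes the difference. For a man who stops at progression and whose participation ends at the 40 (+7) day visit counted from the last dose, the shortfall is about 166 to 173 days.

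This rests on two assumptions: that participation ends with the last required follow-up contact, since the protocol gives no patient-level definition, and that donation is meant to fall under the same precaution as conception. Men are eligible (inclusion criterion 2). That few are likely to be affected is also an assumption. No endpoint, estimate or analysis is touched, so this is a minor, worthwhile improvement.

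**What to change.** Extend the sperm donation sentence in synopsis criterion 14, Section 3.1.1 criterion 14 and Appendix C so that the ban runs through participation and for at least 7 months after the last dose. Check that the consent form gives the same instruction. If a shorter donation period is intended, the medical team should state it.

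The cost is one phrase in three places at the next amendment, a consent form check, and a slightly longer restriction for a few men.
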